2.9.4.3 Other safety assessments

Serum and urine pregnancy test results (if applicable) will be listed for female patients. All data from chest X-ray examination, auditory test, ocular assessment, hepatitis testing, and pregnancy test will be listed for the FAS.

Descriptive statistics for blood transfusion data during the treatment phase (on-treatment period) will be provided by visit (see Table 2-2 for time windows definition) for the Safety Set:

- platelets (amount transfused [mL], hematocrit of blood transfused [%])
- packed RBC (PRBC) (amount transfused [mL], hematocrit of blood transfused [%])
- whole blood (amount transfused [mL], hematocrit of blood transfused [%])

Summary statistics for the number of transfusions (platelets, PRBC, whole blood) per patient will be presented by frequency distribution (number of patients with 1 unit transferred, number of patients with 2 units transferred, on up to the maximum number of units transferred for any one patient) and visit (see Table 2-2 for time windows definition).

Note: Each blood transfusion will be recorded separately on the Blood transfusion - During treatment phase eCRF, therefore the sum of each of the blood transfusion parameters of interest which occur during the time window of interest will be presented.

Data related to blood transfusion during the treatment phase will be listed by center and patient number for the FAS.

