2.3.3.2 Laboratory data and vital signs

Laboratory data (biochemistry, hematology, and urinary parameters as well as serum creatinine, creatinine clearance, and proteinuria) and vital signs will be collected at screening visits, regular patient visits, and EOT.

If two or more assessments are performed within a time window then the assessment closest to the planned visit will be used in analyses by time window. When two values are equidistant from the planned assessment, the later one will be used in analyses.

Note: For worst post-baseline assessment, all on-treatment values are considered regardless of time windows. Table 2-2 shows the defined time windows, where a month is regarded as 4 weeks.

Table 2-2 Time windows for laboratory and vital signs data

Time window	Planned visit timing	Time window definition
On-treatment		
Baseline	On or before Study Day 1*	≤ Study Day 1*
Week 2	Study Day 15	Study Day 2 to Study Day 21
Month 1	Study Day 29	Study Day 22 to Study Day 43
Month 2	Study Day 57	Study Day 44 to Study Day 71
Month 3	Study Day 85	Study Day 72 to Study Day 99
Month 4	Study Day 113	Study Day 100 to Study Day 127
Month 5	Study Day 141	Study Day 128 to Study Day 155
Month 6	Study Day 169	Study Day 156 to Study Day 183
Month 7	Study Day 197	Study Day 184 to Study Day 211
Month 8	Study Day 225	Study Day 212 to Study Day 239
Month 9	Study Day 253	Study Day 240 to Study Day 267

Time window	Planned visit timing	Time window definition
Month 10	Study Day 281	Study Day 268 to Study Day 295
Month 11	Study Day 309	Study Day 296 to Study Day 323
Month 12	Study Day 337	Study Day 324 to Study Day 351
Month 13	Study Day 365	Study Day 352 to Study Day 379
Month 14	Study Day 393	Study Day 380 to Study Day 407
Month 15	Study Day 421	Study Day 408 to Study Day 435
Month 16	Study Day 449	Study Day 436 to Study Day 463
Month 17	Study Day 477	Study Day 464 to Study Day 491
Month 18	Study Day 505	Study Day 492 to Study Day 519
Month 19	Study Day 533	Study Day 520 to Study Day 547
Month 20	Study Day 561	Study Day 548 to Study Day 575
Month 21	Study Day 589	Study Day 576 to Study Day 603
Month 22	Study Day 617	Study Day 604 to Study Day 631
Month 23	Study Day 645	Study Day 632 to Study Day 659
Month 24	Study Day 673	Study Day 660 to Study Day 687
Month 25	Study Day 701	Study Day 688 to Study Day 715
Month 26	Study Day 729	Study Day 716 to Study Day 743
Month 27	Study Day 757	Study Day 744 to Study Day 771
Month 28	Study Day 785	≥ Study Day 772
EOT		

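### SAP 2.9.4.3 adds hematocrit percentages across transfusions, and its volume and unit totals cannot be compared between the shorter early windows and the later ones

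*SAP*

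**What the plan says.** SAP 2.9.4.3 (Other safety assessments) plans descriptive statistics of on-treatment transfusions for the Safety Set, by Table 2-2 window. It covers platelets, packed red cells and whole blood, each with the same two parameters. The packed-red-cell entry reads "packed RBC (PRBC) (amount transfused [mL], hematocrit of blood transfused", with percent as the unit of the second. A note explains that transfusions are recorded one by one, "therefore the sum of each of the blood transfusion parameters of interest which occur during the time window of interest will be presented". A frequency distribution of units per patient is also planned: "number of patients with 1 unit transferred, number of patients with 2 units transferred, on up to the maximum number of units transferred".

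Table 2-2 (SAP 2.3.3.2) defines Week 2 as "Study Day 2 to Study Day 21", Month 1 as "Study Day 22 to Study Day 43" and Month 2 as "Study Day 44 to Study Day 71". Months 3 to 27 follow in steps of the same length as Month 2. Month 28 is "≥ Study Day 772", with no upper limit. The same section says the windows serve to pick one laboratory or vital-sign value per visit, the one nearest its planned day.

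Nothing in SAP 2.9.4.3 scales a total for window length or for days observed. The protocol has no transfusion analysis that would take precedence.

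**The concern.** There are two separate problems. First, the instruction to sum covers every listed parameter, and one of them is a concentration. A programmer who follows the text will add percentages. Patients with one transfusion in a window will show a real hematocrit and patients with two or more will show a number that is not one. The table will not mark which is which.

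Second, windows built to select a single value near a visit are used here to accumulate events. The first two are shorter than the rest, so totals can step up after Month 1 without any change in transfusion practice. The trial has a single arm, so there is no control column in which the same step would appear and be recognised.

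Transfused red cells are the iron input against which serum ferritin, the only efficacy measure, is read. This table is the planned summary of the volume of that input, so a reader may well turn to it.

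**Working it through.** The plan states no figure of its own to reproduce.

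**Window lengths** (last day - first day + 1, from Table 2-2)
- Week 2: 21 - 2 + 1 = 20 days
- Month 1: 43 - 22 + 1 = 22 days
- Month 2: 71 - 44 + 1 = 28 days; Months 3 to 27 are also 28 days

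**Totals at a constant rate, averaged over all patients**

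A constant rate is a fair starting point, because Protocol 6.4.2 has patients continue their pre-enrollment transfusion regimen. Expected total = rate × window length, so the ratios do not depend on the rate:
- Week 2 to Month 1: 22/20 = 1.10
- Month 1 to Month 2: 28/22 = 1.27
- Week 2 to Month 2: 28/20 = 1.40

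For illustration, take 8 units a year, the minimum anticipated in the parent-study criteria (Protocol 5.2). Expected units = 8 × length / 365.25, which gives 0.438, 0.482 and 0.613. Rescaled to 28 days, 0.438 × 28/20, 0.482 × 28/22 and 0.613 all equal 0.613, so the step disappears.

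**If only transfused patients are averaged**

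Regular regimens were enumerated over every starting day, at constant volume per transfusion. Entries are Week 2 / Month 1 / Month 2.

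| Interval | Mean, all patients | Share transfused | Mean, transfused only |
|---|---|---|---|
| 14 days | 1.43 / 1.57 / 2.00 | 100% / 100% / 100% | 1.43 / 1.57 / 2.00 |
| 21 days | 0.95 / 1.05 / 1.33 | 95% / 100% / 100% | 1.00 / 1.05 / 1.33 |
| 28 days | 0.71 / 0.79 / 1.00 | 71% / 79% / 100% | 1.00 / 1.00 / 1.00 |

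From Week 2 to Month 2 the mean among transfused patients rises 40%, 33% and 0% respectively. Whatever is missing from the 40% appears as a rise in the share transfused.

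**Hematocrit**

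For k transfusions with mean hematocrit h, the planned entry is k × h. With k = 2 it passes 100% when h > 50%. The documents give no value for h, so a range is assumed:
- h = 55%: two sum to 110%, three to 165%
- h = 60%: 120% and 180%
- h = 70%: 140% and 210%

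Compare a volume-weighted mean for two assumed units, 280 mL at 55% and 320 mL at 65%: (280 × 55 + 320 × 65) / 600 = 36,200 / 600 = 60.3%. The planned sum is 55 + 65 = 120%.

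**Patients with no transfusion**

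At 8 units a year, and assuming a Poisson count, the share with none is exp(-mean): exp(-0.438) = 0.645, exp(-0.482) = 0.618 and exp(-0.613) = 0.542. At that minimum rate more than half the patients would have no unit in a window, so how they are counted matters to the table.

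**The case against.** The best defence is that the sum was meant only for volumes and unit counts. That may be so, but the text says each parameter and hematocrit is one of the two listed, so the wording still needs correcting.

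The other objections limit the point, and most of them stand:

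- **Size of the step.** A reader might infer that the tabulated mean will rise 40% whatever the regimen. That holds in full only if untransfused patients enter as zero. SAP 2.1 bases n on non-missing observations and the note refers to transfusions that occur, so they may be left out. The range is then 0-40%.
- **Ferritin time points.** A reader might infer that the unequal windows distort the setting in which ferritin is read at Months 6 and 12. They do not: Months 2 to 27 are all 28 days long.
- **Month 28.** The open end has no effect for a patient on schedule. Twenty-four calendar months end at about Day 731. Adding the 7-day visit tolerance and the 30-day on-treatment tail gives about Day 768, before Day 772.
- **Other summaries.** It would be too strong to call this the only planned on-treatment summary of transfusion. Protocol 6.4.1 has transfusions listed on the concomitant medication form, and SAP 2.5.2 counts patients with concomitant non-drug therapies. That gives a number of patients but no volume. SAP 2.9.4.3 also plans a listing.
- **Zero units.** The categories begin at 1 unit, but the text does not say that untransfused patients leave the denominator. This is an ambiguity to settle, not a demonstrated error.

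**Conclusion.** The hematocrit instruction is wrong as written. It gives an invalid value whenever a patient has two or more transfusions of one product in a window, and a value above 100% when two such transfusions average more than 50%. The first statement needs no assumption. The 110-140% illustration rests on an assumed packed-red-cell hematocrit of 55-70%.

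Volume and unit totals are not comparable between Week 2, Month 1 and the later windows. At a constant rate, the all-patient mean rises 27% from Month 1 to Month 2 and 40% from Week 2 to Month 2. Among transfused patients only, the Week 2 to Month 2 rise is 0-40%, and the rest shows up in the share transfused. Comparisons among fully observed Months 2 to 27 are unaffected.

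This concerns one descriptive safety table. No primary or secondary endpoint calculation changes, and the documents do not support reading it as a flaw in the ferritin analysis.

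**What to change.** Amend SAP 2.9.4.3 as follows:

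1. Restrict the sum to volume and number of units.
2. Report hematocrit as a volume-weighted mean per patient and window, for packed red cells and whole blood, using transfusions with both values recorded and showing how many lack one. Drop it for platelets.
3. Express volume and units per observed day, or per 28 days, so that short and partly observed windows are comparable.
4. State that patients still under observation with no transfusion count as 0 units and stay in the denominator, and add that row to the distribution.

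The cost is SAP wording and programming. Amount and hematocrit are already planned data items, although the documents do not show how completely hematocrit is recorded.

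Optionally, as a new analysis and not a correction, report red-cell volume (mL × hematocrit/100) per kg per day from Baseline to Month 6 and to Month 12, as context for the ferritin change. Weight is already collected at Visit 1 and from Visit 3 onward (Protocol Table 7-1).

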2.10 Pharmacokinetic endpoints

There are no pharmacokinetic (PK) endpoints in this study.

2.11 Pharmacodynamic and PK/Pharmacodynamic analyses

There are no pharmacodynamic and PK/pharmacodynamic analyses planned in this study.

2.12 Patient-reported outcomes

There are no patient-reported outcomes (PRO) analyses planned in this study.

2.13 Biomarkers

There are no biomarker analyses planned in this study.

2.14 Other exploratory analyses

There are no other exploratory analyses planned in this study.

2.15 Interim analysis

There are no interim analyses in this study.

3 Sample size calculation

No formal sample size has been calculated. All patients enrolled into CICL670F2201 who have completed 24 weeks treatment will be offered participation in this current protocol and those consenting to participate will contribute to the pool of data.

According to enrolment of CICL670F2201 in Region Europe, a maximum of 90 patients should be eligible for enrollment in this study. However as only three countries (Austria, Greece, and Italy) are participating in this study which is less than originally foreseen, it is planned to enroll a maximum of 58 patients.

4 Change to protocol specified analyses

Due to insufficient patient numbers in the categories for the subgroups: age and main underlying disease, it was agreed to remove the planned age and main underlying disease subgroup analyses.

Within the protocol, it is stated that the Baseline serum ferritin value will be defined as the average of the 2 measurements obtained during the Screening period. It was clarified that this statement is in reference to the eligibility criteria and baseline serum ferritin should be derived for analysis purposes as outlined in Section 2.3.2.

5 Appendix

5.1 Imputation rules

5.1.1 AE date imputation

5.1.1.1 AE end date

For the purpose of date imputation, the study treatment follow-up period date is defined as the last available visit date, i.e. including unscheduled visits after the end of study visit.

- 1. If the AE end date month is missing, the imputed end date should be set to the earliest of the (study treatment follow-up period date, 31DECYYYY, date of death).
- 2. If the AE end date day is missing, the imputed end date should be set to the earliest of the (study treatment follow-up period date, last day of the month, date of death).
- 3. If AE year is missing or AE is ongoing, the end date will not be imputed.

If the imputed AE end date is less than the existing AE start date then use AE start date as AE end date.

5.1.1.2 AE start date

AEs with completely missing onset dates will be considered to be treatment emergent. AEs with partially missing onset dates will also be included as treatment emergent when the month (if it exists) and the year occur on or later than the month and year of first administration of study treatment within this study.

Partial AE start dates are imputed with reference to the first administration of study treatment (TRTSTD) within this study as outlined in the table below.

The date value is split into day, month, year sections and referenced in the imputation table as outlined below

Month

Year

Dav

		- Duj	Mondi	1001
Partial AE Start Dat	te	Not used	MON	YYYY
Treatment Start Da	te (TRTSTD)	Not used	TRTM	TRTY
The following matr	rix explains the logi	ic behind the imputa	ation.	
Comparison of month section	MON missing	MON <trtm< td="">MON=TRTM	MON>TRTM	</trtm<>	MON=TRTM	MON>TRTM
YYYY missing	NC	NC	NC	NC
YYYY <trtm< td="">(D) =	(C) =	(C) =	(C) =	</trtm<>	(D) =	(C) =	(C) =	(C) =
	01JULYYYY	15MONYYYY	15MONYYYY	15MONYYYY
	Before Treatment	Before Treatment	Before Treatment	Before Treatment
	Start	Start	Start	Start
YYYY=TRTY	(B) =	(C) =	(A)	(A)
	TRTSTD+1	15MONYYYY	= TRTSTD+1	= 01MONYYYY
	Uncertain	Before Treatment	Uncertain	After Treatment

Comparison of month section	MON missing	MON <trtm< td="">MON=TRTM	MON>TRTM	</trtm<>	MON=TRTM	MON>TRTM
		Start		Start
YYYY>TRTY	(E) =	(A)	(A)	(A)
	01JANYYYY	= 01MONYYYY	= 01MONYYYY	= 01MONYYYY
	After Treatment	After Treatment	After Treatment	After Treatment
	Start	Start	Start	Start

Page 29

CICL670AIC04

The following table is the legend to the logic matrix.

Relationship	
Before Treatment start	Partial date indicates AE start date prior to Treatment Start Date in this study
After Treatment start	Partial date indicates AE start date after Treatment Start Date in this study
Uncertain	Partial date insufficient to determine relationship of AE start date to Treatment Start Date in this study
Imputation calculation	
NC/Blank Uncertain	No convention
(A) After Treatment Start or Uncertain	MAX(01MONYYYY, TRTSTD+1)
(B) Uncertain	TRTSTD+1
(C) Before Treatment Start	15MONYYYY
(D) Before Treatment Start	01JULYYYY
(E) After Treatment Start	01JANYYYY

Before imputing the AE start date, find the AE start reference date.

- If the AE end date is complete and the (imputed) AE end date < TRTSTD then AE start reference date = min (study informed consent date, earliest visit date).
- Else AE start reference date = TRTSTD

To impute AE start date:

- 1. If the AE start date year value is missing, the date uncertainty is too high to impute a rational date. Therefore, if the AE year value is missing, the imputed AE start date is set to NULL.
- 2. If the AE start date year value is less than the study treatment start date year value, the AE started before study treatment. Therefore:
 - a. If AE month is missing, the imputed AE start date is set to the mid-year point (01JULYYYY).
 - b. Else if AE month is not missing, the imputed AE start date is set to the mid-month point (15MONYYYY).
- 3. If the AE start date year value is greater than the study treatment start date year value, the AE started after study treatment. Therefore:

- a. If the AE month is missing, the imputed AE start date is set to the year start point (01JANYYYY).
- b. Else if the AE month is not missing, the imputed AE start date is set to the later of (month start point (01MONYYYY), AE start reference date + 1 day).
- 4. If the AE start date year value is equal to the study treatment start date year value:
 - a. And the AE month is missing the imputed AE start date is set to the AE reference start date + 1 day.
 - b. Else if the AE month is less than the study treatment start month, the imputed AE start date is set to the mid-month point (15MONYYYY).
 - c. Else if the AE month is equal to the study treatment start date month or greater than the study treatment start date month, the imputed AE start date is set to the later of (month start point (01MONYYYY), AE start reference date + 1 day).

If complete (imputed) AE end date is available and the imputed AE start date is greater than the (imputed) AE end date, then imputed AE start date should be set to the (imputed) AE end date.

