2.6.1 Primary endpoint

The primary variables are:

- treatment emergent AEs (TEAEs)
 - An AE is defined as treatment emergent if its onset date is on or after (≥) the first administration of study treatment within this study or events present prior to start of study treatment but increased in severity on or after (≥) the first administration of study treatment within this study but not later than 30 days after the last study treatment in this study (i.e. during the safety observation period, see Section 2.1 for definition).
- changes from baseline at Months 6 and 12 for the following laboratory assessments:
 - serum creatinine
 - creatinine clearance
 - ALT/SGPT
 - AST/SGOT
 - red blood cell (RBC)
 - platelets

• white blood cell (WBC)

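### SAP 5.1.1.2 makes an AE with no onset date treatment-emergent even if it ended before first dose, and for partial onsets its opening rule conflicts with its own imputation steps and the 30-day limit

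*SAP*

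**What the plan says.** SAP 5.1.1.2 opens with two classification sentences. The first is unconditional: "AEs with completely missing onset dates will be considered to be treatment emergent". The second reads "AEs with partially missing onset dates will also be included as treatment emergent when the month (if it exists) and the year occur" no earlier than the month and year of first dose. Neither mentions the AE end date or the end of the on-treatment window.

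The same section then gives numbered imputation steps. Step 1 deals with a missing year: "Therefore, if the AE year value is missing, the imputed AE start date is set to NULL". Before the other steps are applied, a reference date is chosen: "If the AE end date is complete and the (imputed) AE end date < TRTSTD then AE start reference date = min" of the consent date and the earliest visit date; otherwise it is the date of first dose (TRTSTD). After the steps there is a cap. If the imputed start falls after the end date, "then imputed AE start date should be set to the (imputed) AE end date".

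SAP 2.6.1 defines the treatment-emergent AE (TEAE) as a primary variable and closes the window with "but not later than 30 days after the last study treatment in this study". SAP 2.9.1 assigns AEs before first dose to the pre-treatment period and AEs more than 30 days after last dose to the follow-up period, for listings only. It summarizes TEAEs alone.

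**The concern.** There are two defects.

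First, an AE with no onset date but a recorded end date before first dose cannot have started on treatment. The opening sentence still makes it a TEAE. Step 1 leaves it without a start date, so the window in 2.6.1 has nothing to act on. The only rule that gives this record a status gives the wrong one.

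Second, for partial onsets the SAP holds two routes to the flag and does not rank them. One is the month-and-year comparison in the opening sentence. The other is the imputed date tested against 2.6.1. Two programmers could each follow the SAP and produce different tables.

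Such records are possible here. Protocol 8.1.1 has AEs recorded from informed consent, and Table 7-1 has two screening visits more than a week apart. SAP 1.1 says that no patient continued directly from CICL670F2201, and the protocol requires a 5-day washout for patients who had switched to other chelation. AE monitoring runs for at least 30 days after last dose, so later events may also be in the database. The flag feeds the primary TEAE incidence with its Clopper-Pearson interval, the exposure-adjusted incidence and the registry tables in SAP 2.9.1.

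**Working it through.** The plan states no figure to reproduce: it has no formal sample size and gives no count of AEs with incomplete dates. The check applies both routes to test records with assumed dates: consent 4 March 2017 (also taken as the earliest visit), first dose 20 March 2017, last dose 10 June 2018. The window therefore closes on 10 June 2018 + 30 days = 10 July 2018.

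- Opening sentences: TEAE if the onset is completely missing, or if the known month and year are on or after March 2017 (year alone: 2017 or later).
- Imputed-date route: impute by steps 1-4, apply the end-date cap, then test 20 March 2017 ≤ start ≤ 10 July 2018.

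| Case | Onset recorded | End date | Opening sentences | Imputed start | Imputed-date route |
|---|---|---|---|---|---|
| A | none | 12 Mar 2017 | TEAE | none | cannot be tested |
| B | Mar 2017 | 12 Mar 2017 | TEAE | 5 Mar 2017 | not TEAE |
| C | 2017 | 12 Mar 2017 | TEAE | 5 Mar 2017 | not TEAE |
| D | Mar 2017 | ongoing | TEAE | 21 Mar 2017 | TEAE |
| E | Sep 2018 | none | TEAE | 1 Sep 2018 | not TEAE |
| F | none | 1 Oct 2018 | TEAE | none | cannot be tested |
| G | 2018 | none | TEAE | 1 Jan 2018 | TEAE |
| H | Feb 2017 | none | not TEAE | 15 Feb 2017 | not TEAE |
| I | Jul 2018 | 25 Jul 2018 | TEAE | 1 Jul 2018 | TEAE |

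Derivations for the cases that matter:

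- B: the end date precedes first dose, so the reference date is 4 March. Step 4c gives the later of 1 March and 4 March + 1 day = 5 March, which is before 20 March.
- C: step 4a gives 4 March + 1 day = 5 March.
- E: step 3b gives the later of 1 September 2018 and 21 March 2017 = 1 September 2018, which is after 10 July 2018.
- A: step 1 gives no start date, so only the opening sentence decides, and it decides TEAE.

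The routes conflict in B, C and E. They agree in D, G, H and I. In A and F only the opening sentence gives a result. That result is wrong in A. It is defensible in F, because an event that ended late may have begun on treatment.

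The imputation matrix in 5.1.1.2 uses first dose + 1 day where the steps use reference date + 1 day. In B and C the matrix gives 21 March 2017, and the cap resets this to 12 March 2017. That is still before first dose, so this mismatch changes no flag here.

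Scale, for one misclassified patient with no other event in the category:

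- N = 58 (planned maximum, SAP section 3): 1/58 = 1.7 percentage points. The 95% Clopper-Pearson interval moves from 0 to 6.2% at 0/58 to 0.0 to 9.2% at 1/58.
- N = 90 (maximum eligible): 1/90 = 1.1 points.
- N = 30 (assumed): 1/30 = 3.3 points.

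**The case against.** The strongest counter-argument is that the checks exist. A reader of the two opening sentences might infer that the SAP never looks at the end date or the 30-day limit, so that pre-dose and late AEs in general enter the primary endpoint. The documents do not support that. The same section has two end-date checks on partial onsets, the reference date and the cap. The 30-day limit stands in 2.6.1 and again in 2.9.1. The syntax of 2.6.1 leaves some doubt whether the limit covers new onsets or only worsened events, but its reference to the safety observation period, and 2.9.1, support both. For partial onsets the defect is therefore unstated precedence. Cases B, C and E reach the endpoint only if the appendix sentence overrides the body's definition, and nothing in the SAP says that it does.

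It is also fair to say that calling an unknown onset treatment-emergent is a conservative default for a safety endpoint, and that case A should be uncommon. Screening is short, conditions present at consent go to medical history, and missing values are queried. This limits the size but does not rescue the rule, because the default is kept when another recorded date rules it out.

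A reader might also infer that these events are attributed to study drug. They are not. Treatment-emergent status concerns timing, and SAP 2.9.1 summarizes suspected relationship separately.

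Finally, patients are counted once per category, so an extra record in a patient who already has an event there changes nothing.

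**Conclusion.** The point holds in two parts. For AEs with a completely missing onset that ended before first dose, the SAP states a rule that gives a wrong flag in a primary variable, and no other provision corrects it. For partial onsets, the SAP contains two rules that disagree in identifiable situations: the AE ended pre-dose in the first-dose month or year, or the known onset lies after last dose + 30 days. It does not say which rule governs. Misclassification of partial onsets is possible but not established.

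The overall effect cannot be sized, because the number of AEs with incomplete onset dates is not given. The 1.7 points per patient assumes that all 58 planned patients are in the denominator and that the patient has no other event in the category. For the any-TEAE incidence, that means no other TEAE over up to 24 months, so the effect is more likely to show in individual terms. The test dates are assumed and serve only to expose the logic.

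**What to change.** Replace the two opening sentences of SAP 5.1.1.2 with text to this effect:

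*For partial onset dates, treatment-emergent status is determined by the start date imputed under steps 1-4, including the end-date cap, tested against the window from first dose to last dose + 30 days in Section 2.6.1. AEs whose onset year is missing are treatment-emergent unless the complete or imputed end date is before first dose.*

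This removes cases A, B, C and E from the TEAE count and keeps F. Using the imputed end date is safe, because SAP 5.1.1.1 takes the end of the known month or year, cut back only by the last visit or death. The lower bound on onset must survive the edit: an AE whose known month and year precede first dose (case H) stays pre-treatment unless it worsened on treatment. A general rule of treatment-emergent unless ruled out would lose that bound.

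Matrix entries (A) and (B) can be aligned with the reference date used in the steps, for consistency only.

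The cost is a few lines of SAP wording and one condition in the derivation of the TEAE flag. No new data are needed.
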